6.1. PRIMARY EFFICACY ENDPOINT

The primary endpoint will evaluate the percent of successful terminations of life-threatening VT or VF in subjects who are enrolled in compliance with the protocol-defined entry criteria and are treated with either model of the Jewel EP Lab System. The endpoint will be achieved if the lower confidence limit exceeds the performance goal of 62% using a one-sided exact lower 97.4% confidence bound at one of three testing points. These conditions ensure that performance will be in line with previously published randomized controlled trial results on a relevant comparator, the ZOLL LifeVest, which is the only commercially approved WCD in Europe or the United States. A sequential method of testing will be used to evaluate conversion success. If the Jewel EP Lab System is NOT used to deliver a defibrillation shock during the EP procedure, the subject will not be included in the treatment analysis.

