For the calculation of sample size, this study will use an anticipated first shock conversion success rate of 87.5% in the EP Lab Study with a performance goal of 62%, the same as the first shock success rate seen in VEST. The performance of the Jewel will be considered acceptable if the lower confidence limit exceeds the performance goal of 62% (green line in the graph on page 24).

The sample size for this study is a maximum of 24 subjects. Subjects can be treated with either the ES-1 or the ES-2 model of the Jewel EP Lab System, as the devices are representative of each other. This sample size is based on a group sequential design measuring the observed proportion of successful life-threatening VT or VF terminations. The group sequential design uses a Pocock alpha spending function and allows for testing after 12, 18, and 24 subjects are enrolled. The design controls the overall Type I error rate at 5%. In line with the Pocock alpha spending function, a one-sided lower 97.4% exact confidence bound will be calculated using the exact binomial (Clopper-Pearson) method at each testing point.

Primary Endpoint Analysis:

Upon completion of the Jewel EP Lab Study, all clinical data from both the ES-1 and ES-2 models of the Jewel EP Lab System will be pooled, as the devices are representative of each other. The primary endpoint will evaluate the percent of successful terminations of life-threatening VT or VF in subjects who are in subjects who are enrolled in compliance with the protocol-defined entry criteria and treated with the Jewel EP Lab System (either ES-1 or ES-2 model).

Using the VEST RCT results for the first shock success as a guide, the performance goal of 62% was established for the Jewel EP Lab Study. The endpoint will be achieved if the lower confidence limit exceeds the performance goal of 62% using a one-sided lower 94.5% exact confidence bound at one of the three testing points.

These conditions ensure that performance will be in line with previously published randomized controlled trial results on a relevant comparator, the ZOLL LifeVest which, is the only commercially approved WCD in Europe or the US. The method for testing the conversion success will follow these steps:

1. If after attempting to convert the first 12 subjects, all subjects have been successfully converted (100% conversion rate) the trial will be stopped and deemed a success. Otherwise, continue to Step 2.

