2. If conversion is less than 100% after 12 total subjects, enroll six (6) additional subjects for a total of 18 subjects. If 17 out of the 18 are successfully converted (94.4% conversion rate), or if 16 out of the 18 are successfully converted (88.0% conversion rate), the trial will be stopped and deemed a success. Otherwise, continue to Step 3.
3. Enroll the final six (6) subjects for a total of 24 subjects. If after attempting to convert 24 subjects, 21 of the 24 are successful (87.5% conversion rate), the trial will be deemed a success.

A 100% conversion rate with 12 subjects results in a one-sided lower 97.4% exact confidence bound of approximately 73.7% which exceeds the 62% performance goal.

[figure not shown]
With a sample size of 18 subjects with 1 failure, the conversion rate is 94.4% with a one-sided lower 97.4% exact confidence bound of approximately 72.8% which also exceeds the 62% performance goal.

With a sample size of 18 subjects with 2 failures, the conversion rate is 88.9% with a one-sided lower 97.4% exact confidence bound of approximately 65.4% which also exceeds the 62% performance goal.

With a sample size of 24 subjects with 3 failures, the conversion rate is 87.5% with a one-sided lower 97.4% exact confidence bound of approximately 67.8% which also exceeds the 62% performance goal.

All of these scenarios result in a successful trial as the one-sided lower 97.4% exact confidence bound is above the performance goal of 62%. If at any point during the course of this study there are more than three (3) failures to convert a shockable rhythm (life-threatening VT or VF) due to the Jewel, the study will be stopped and deemed unsuccessful.

The graph below summarizes the group sequential study design, conversion success, and results of the one-sided lower 97.4% exact confidence bound.

Overall Type I Error Discussion:

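### The primary success sentence in Section 11.1 prints a 94.5% bound where the rest of the plan uses 97.4%; correct it, and settle 20/24 in the same edit

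*Combined protocol and SAP*

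**What the plan says.** The success criterion is stated twice, at different levels. Section 6.1 requires the lower limit to exceed "62% using a one-sided exact lower 97.4% confidence bound at one of three testing points". The Primary Endpoint Analysis in Section 11.1 requires it to exceed "62% using a one-sided lower 94.5% exact confidence bound at one of the three testing points".

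The design paragraph of Section 11.1 says that "a one-sided lower 97.4% exact confidence bound will be calculated using the exact binomial (Clopper-Pearson) method at each testing point". After the steps, 97.4% appears six more times: with the four worked bounds, in the sentence summarising them and in the sentence introducing the graph. That makes eight statements of 97.4% and one of 94.5%.

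Directly after the 94.5% sentence comes a procedure in counts: "The method for testing the conversion success will follow these steps". Step 1 stops for success at 12 subjects only if "all subjects have been successfully converted (100% conversion rate) the trial will be stopped and deemed a success. Otherwise, continue to Step 2". Step 2 accepts 17 or 16 of 18. Step 3 reads "If after attempting to convert 24 subjects, 21 of the 24 are successful (87.5% conversion rate), the trial will be deemed a success". The study is also stopped as unsuccessful once more than three conversion failures are due to the Jewel.

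**The concern.** Two sentences that should be identical set different thresholds for the primary endpoint, and the one in the analysis section is the looser. If it were applied, a trial could be declared successful on a result that the steps treat as inconclusive, and the claimed 5% control of type I error would no longer hold. The document therefore has to show which level is intended.

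A related question is whether the criterion and the steps agree once the level is settled. A bound rule and a list of counts are interchangeable only if they accept the same results at every look.

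**Working it through.** **Inputs, all from Section 11.1 unless noted.** Performance goal 62%; anticipated success 87.5%; looks at 12, 18 and 24 subjects; stated overall type I error 5%; levels 97.4% (also Section 6.1) and 94.5%; accepted counts 12/12, 16/18 or 17/18, 21/24; stop at more than three failures due to the Jewel.

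**1. Which level produced the printed bounds?** The one-sided Clopper-Pearson lower bound for x successes in n is the α quantile of a Beta(x, n − x + 1) distribution, with α = 0.026 for 97.4% and 0.055 for 94.5%. For 12/12 it reduces to α^(1/12): 0.026^(1/12) = 0.738 and 0.055^(1/12) = 0.785.

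| Result | Printed | At 97.4% | At 94.5% |
|---|---|---|---|
| 12/12 | 73.7% | 73.78% | 78.53% |
| 17/18 | 72.8% | 72.90% | 76.74% |
| 16/18 | 65.4% | 65.49% | 69.51% |
| 21/24 | 67.8% | 67.81% | 71.23% |

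The plan's text, for example "12 subjects results in a one-sided lower 97.4% exact confidence bound of approximately 73.7"% and "the conversion rate is 88.9% with a one-sided lower 97.4% exact confidence bound of approximately 65.4"%, fits 97.4% within 0.1 point and does not fit 94.5%. As a cross-check, a constant Pocock boundary for looks at information 0.5, 0.75 and 1 with one-sided α = 0.05 has critical value 1.947 and nominal α 0.02576, that is 97.42%.

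**2. Which level agrees with the steps?** The borderline results against 62% are:

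| Result | At 97.4% | At 94.5% | Steps |
|---|---|---|---|
| 11/12 | 61.77%, fails | 66.80%, passes | continue |
| 15/18 | 58.78%, fails | 62.88%, passes | continue |
| 20/24 | 62.79%, passes | 66.29%, passes | not listed |

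At 97.4% the bound and the steps agree at 12 and 18 subjects. At 94.5% they disagree at both. At 24 they disagree under either level.

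**3. Type I error at a true rate of 62%**, by exact binomial enumeration over the three looks, each term being success first reached at that look:

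- Listed counts (12/12, 16/18, 21/24): 0.0032 + 0.0108 + 0.0019 = 0.0160 (unrounded sum), with or without the failure stop. The first term is 0.62^12. The second is P(at least 16/18) = 0.0127, less the part already stopped at 12/12.
- 94.5% read literally (11/12, 15/18, 20/24): 0.0270 + 0.0305 + 0.0041 = 0.0616 without the stop. With the stop, and all failures due to the Jewel, the last term vanishes, because a trial not successful at 18 already has at least four failures. That leaves 0.0575.

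**4. Success at a true rate of 87.5%**, all failures due to the Jewel: 0.8308 under the literal 94.5% rule and 0.7051 under the counts. The difference, 0.1257, is made up of trials the sentence passes and the steps do not: 0.0362 pass at 11/12 and 0.0895 pass at 15/18.

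**5. The 20/24 gap that remains at 97.4%.** It needs four failures in 24, no earlier success, and at least one failure not due to the Jewel. The documents give no rate for such failures, so the shares below are assumptions, taken as independent between subjects. Here the 97.4% bound governs alongside the stop.

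| Assumed share of failures not due to the Jewel | Trials ending at 20/24 (true rate 87.5%) | Success at 87.5% | Type I error |
|---|---|---|---|
| 0% | 0% | 70.5% | 1.6% |
| 5% | 2.5% | 73.0% | 1.8% |
| 10% | 4.5% | 75.1% | 2.0% |
| 25% | 9.0% | 79.5% | 2.4% |
| Stop never triggers (ceiling) | 13.2% | 83.7% | 2.75% |

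**The case against.** The best defence is that nobody would act on 94.5%. The design paragraph fixes 97.4% for every look, the steps give explicit counts, and every worked bound is at 97.4%. An analyst would have to stop at 11/12 although Step 1 demands 12/12. The 5.75% and 12.6% therefore describe a rule that the procedure excludes, and they should not be read as expected harm. That is fair and limits the severity. It does not remove the need to correct the formal criterion, since the error runs in the sponsor's favour and would invite dispute if 11/12 or 15/18 were observed.

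On 20/24, the defence is that the issue is separate from the misprint, which is true: 20/24 clears 62% at either level. It is also argued that only subjects who received a Jewel shock enter the treatment analysis, so every failure there is naturally one due to the Jewel and the stop always applies. That reading is reasonable and makes the gap zero. However, the qualifier in the stop allows another reading, and the text does not say who attributes failures or how. The graph is not available in the text reviewed and might show the boundary at 24 subjects, so the absence of a precedence rule is established for the readable text only.

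**Conclusion.** The concern holds. The 94.5% is wrong as printed: it stands alone against eight statements of 97.4%, reproduces none of the printed bounds and conflicts with Steps 1 and 2. Taken literally it exceeds the stated type I error by 0.75 point with the failure stop, or by 1.2 points without it. The listed counts, if followed, stay well inside 5%. These figures are exact and assume only independent subjects with a common success rate, plus, where the stop is applied, that all failures are due to the Jewel.

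The 20/24 discrepancy is secondary. It is real only if some failure is attributed to something other than the Jewel, and its size depends on a rate that the documents do not give. The correction should be made, but it does not call the design into question.

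**What to change.** In the Primary Endpoint Analysis sentence of Section 11.1, replace 94.5% with 97.4%. This changes one number and leaves the design untouched.

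In the same edit, make Section 6.1 and Step 3 agree on 20/24. The choice that follows the plan's own stepwise procedure is to add to both places:

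> Success is decided by the counts in Steps 1 to 3 (12/12; at least 16/18; at least 21/24). The 97.4% exact bound is reported with the result. 20/24 is not a success, whatever the cause of the failures.

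State its operating characteristics beside it: type I error 1.6%, and success probability 70.5% at a true rate of 87.5%. If the sponsor prefers the 97.4% bound to govern, Step 3 should say so for 20/24, and the figures for that rule should be given (at most 83.7% success and 2.75% type I error). This clause is one sentence but a genuine choice.

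Either figure is below the 90% power stated in the Overall Type I Error Discussion, so that statement will need reconciling as a separate matter. The looks, the maximum of 24 subjects and the data collected do not change.

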The group sequential design of the Jewel EP Lab Study is meant to control the overall Type I error rate with 90% power. This design uses a Pocock alpha spending approach which controls the overall Type I error rate at 5%. The group sequential design of the Jewel EP Lab Study is being used in order to reduce the number of subjects put at risk through early stopping rules, while still providing sufficient data to demonstrate the effectiveness of the Jewel EP Lab System to successfully convert life-threatening VT and VF. Preliminary testing points and alpha expenditures were estimated using SAS version 9.3 which employs a normal approximation to designing sequential trials. The alpha spent at each testing point was used to determine the confidence level of the exact lower confidence bound. These confidence levels were then used to adjust the testing points to accommodate exact methods rather than the normal approximation. Simulations of 3000 trials of size 24 were used to confirm that the Type I error rate was controlled at the 5% level.

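### The 97.4% bounds serve the look-by-look decision, but Section 11.1 plans no bound or estimate of the final conversion rate that allows for stopping

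*Combined protocol and SAP*

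**What the plan says.** Section 11.1 sets out the design: "The group sequential design uses a Pocock alpha spending function and allows for testing after 12, 18, and 24 subjects are enrolled". On error control it states: "The design controls the overall Type I error rate at 5" per cent. It ties the confidence level to the design: "In line with the Pocock alpha spending function, a one-sided lower 97.4% exact confidence bound will be calculated". The method is Clopper-Pearson, applied at every look. The discussion of Type I error adds: "The alpha spent at each testing point was used to determine the confidence level of the exact lower confidence bound".

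The trial succeeds at 12/12, at 17/18 or 16/18, or at 21/24. It stops as unsuccessful once more than three failures are attributed to the device. The printed bounds are 73.7%, 72.8%, 65.4% and 67.8% in that order; for the last of these the text reads: "the conversion rate is 87.5% with a one-sided lower 97.4% exact confidence bound of approximately 67.8" per cent. Nothing in Section 11.1 describes an estimate or bound that depends on how the sample size was reached, or says what confidence attaches to the bound reported once the trial has stopped.

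Two figures conflict. The success criterion under Primary Endpoint Analysis uses 94.5%, while Section 6.1 and the rest of Section 11.1 use 97.4%. Step 2 reads "16 out of the 18 are successfully converted (88.0% conversion rate"), while the later text gives 88.9% for the same count.

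**The concern.** The primary endpoint is a percentage, so the rate and its bound will be published and compared in size with the 62% goal. Clopper-Pearson is exact when the sample size is fixed in advance. Here 21/24 can be reached only after missing success at both 12 and 18, and the formula does not use that fact. A reader of the final report would naturally take the 97.4% bound as the confidence statement for the final rate, which the plan does not support. If no adjusted estimator is named now, any later choice would be made with the data in view.

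**Working it through.** **Inputs (Section 11.1).** Looks at 12, 18 and 24; the success counts and failure stop above; level 97.4%; goal 62%; anticipated rate 87.5%. Assumed: independent outcomes with a common true rate p, only treated subjects counted, and stopping at the fourth failure. Write q = 1 − p.

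**1. The plan's own bounds.** The lower bound is the Beta(x, n − x + 1) quantile at α. A one-sided Pocock boundary with information 0.50, 0.75 and 1.00 and overall α 0.05 has z = 1.947, so the nominal α is 0.02576, that is 97.4%. This gives 73.72%, 72.85%, 65.44% and 67.77%, within 0.1 point of all four printed bounds. The level is therefore already adjusted for three looks.

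**2. Probability of each success outcome.** 18/18 and 22 or more of 24 cannot occur, because the trial would already have stopped. Counting paths:
- 12/12: p¹²
- 17/18: 12 p¹⁷q (the failure is among the first 12)
- 16/18: (153 − 15) p¹⁶q² = 138 p¹⁶q²
- 21/24: (816 − 20) p²¹q³ = 796 p²¹q³ (three failures by 18, not all in subjects 13 to 18, none afterwards)

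At p = 0.62: 0.00323 + 0.00135 + 0.00950 + 0.00191 = 0.0160. Type I error is 1.6%, below 5%.

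**3. Coverage of the bound reported at stopping.** Just below the 17/18 bound, only 12/12 and 17/18 have bounds above p. Non-coverage is then p¹² + 12p¹⁷q. At p = 0.7285 (α = 0.02576) this is 0.0224 + 0.0149 = 0.0373, so coverage is about 96.3%. With α = 0.026 exactly, coverage is 96.24%. Taken jointly over all three looks, coverage is at least 95.27%.

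**4. Stage-wise ordering.** Rank the success outcomes 12/12, 17/18, 16/18, 21/24 and add their probabilities down to the one observed. Set the sum to 0.05 for the 95% bound and to 0.5 for the median-unbiased estimate. For 21/24, p¹² + 12p¹⁷q + 138p¹⁶q² + 796p²¹q³ = 0.05 at p = 0.677.

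| Outcome | Raw | Printed bound | Stage-wise 95% bound | Median-unbiased, n fixed | Median-unbiased, stage-wise | Due to stopping |
|---|---|---|---|---|---|---|
| 12/12 | 100% | 73.7% | 77.9% | 94.4% | 94.4% | 0.0 |
| 17/18 | 94.4% | 72.8% | 74.5% | 90.8% | 90.3% | 0.5 |
| 16/18 | 88.9% | 65.4% | 68.6% | 85.4% | 85.3% | 0.1 |
| 21/24 | 87.5% | 67.8% | 67.7% | 84.9% | 83.5% | 1.4 |

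Only the printed bounds and the fixed-sample formula behind them put 21/24 ahead of 16/18 on the lower limit. The raw rate, the stage-wise bound and the median-unbiased estimate all put it behind.

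**5. The raw rate given success.** At p = 0.875 the outcome probabilities are 0.2014, 0.1550, 0.2546 and 0.0941, total 0.7051. The mean reported rate is (0.2014 × 1 + 0.1550 × 0.9444 + 0.2546 × 0.8889 + 0.0941 × 0.875)/0.7051 = 93.1%, or 5.6 points above the truth. A fixed 24-subject trial requiring at least 21 successes gives 91.5%, already 4.0 points above. Stopping adds 5.6 − 4.0 = 1.6 points. Over all trials, successful or not, bias at 87.5% is −0.03 points with stopping at the fourth failure, or +0.65 if the failure stop acts only at looks.

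**6. The 94.5% level.** Requiring a 94.5% bound above 62% at each look, with no failure stop, gives a Type I error of 6.2%. This level does not reproduce the printed bounds: it gives 78.5%, 76.7%, 69.5% and 71.2%.

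**The case against.** The strongest defence is that the plan never claims 97.4% as confidence after stopping. It applies that level at each testing point and derives it from the alpha spent there. At the design's overall 95%, three of the four printed bounds are conservative by 1.7 to 4.2 points, and the fourth differs by 0.1. This is a feasibility study of at most 24 subjects and no decision changes. All of that stands.

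Three stronger readings are tempting, and the documents do not support them:
- A reader might infer that the bounds ignore the sequential design. Section 11.1 says otherwise, and step 1 confirms it.
- A reader might set the printed 67.8% for 21/24 against a stage-wise bound at 97.4%, which is 64.4%, and call it overstated by 3.4 points. That adjusts twice, since 97.4% already pays for three looks.
- A reader might blame the 5.6-point excess on stopping. Most of it is ordinary selection on success.

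The median-unbiased estimate has limits too. Most of its distance from the raw rate comes from its convention for discrete data: at 12/12 it is 0.5^(1/12) = 94.4% with or without looks, whereas the minimum-variance unbiased estimate stays at 100%. It does not remove selection on success. Given success, its mean is 87.6% at a true 80%, and at a true 95% it is 91.6%, further from the truth than the raw 96.4%. That is a reason to show it beside the raw rate and not in its place.

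**Conclusion.** The point holds as one about reporting. The pass/fail rule is sound here: Type I error is 1.6% at 62%, and every stage-wise bound exceeds the goal. What is missing is a statement of the confidence attached to the final bound, and an estimate that allows for stopping. Read as a post-stopping limit, the 97.4% bound can fall to about 96.3% coverage, a shortfall of about 1.1 points, and it ranks 21/24 above 16/18. The effect of stopping on the estimate is at most about 1.4 points.

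These figures rest on the count rule as written, independent outcomes with a common rate, and stage-wise ordering. Section 11.1 mentions a prospective SAP; only the content reproduced in the combined document could be assessed.

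**What to change.** Keep the count rule for the decision, and change Section 11.1 as follows:
- State that 97.4% is the look-wise decision level, with 95% overall, and label the printed bounds accordingly.
- Pre-specify, beside the raw rate, the exact one-sided 95% lower bound under stage-wise ordering: 77.9% for 12/12, 74.5% for 17/18, 68.6% for 16/18 and 67.7% for 21/24.
- Pre-specify one stopping-adjusted estimate. The median-unbiased one gives 94.4%, 90.3%, 85.3% and 83.5%. The minimum-variance unbiased one (100%, 91.7%, 87.7%, 82.9%) is an acceptable alternative, provided the choice is made now.
- Reconcile 94.5% in the success criterion with 97.4% elsewhere.
- Correct 88.0% to 88.9% for 16/18 in step 2.

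The cost is wording and a short program, with no patients. The downside is a somewhat lower adjusted rate printed beside the raw one. If the actual stopping point departs from the written rule, the tabulated values must be recalculated.

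### The stated 90% power is not delivered by the written success rule (exact power 70.5% at 87.5%), and the endpoint wording departs from the step counts on the confidence level and on 20/24

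*Combined protocol and SAP*

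**What the plan says.** Section 11.1 sizes the study on an anticipated first-shock success rate of 87.5% against a performance goal of 62%, with Pocock spending and looks after 12, 18 and 24 subjects. It states: "The design controls the overall Type I error rate at 5" per cent. The Overall Type I Error Discussion in 11.1 adds a power of 90% and names no alternative rate.

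Success is described in three ways:

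- **Bound.** Section 6.1: "The endpoint will be achieved if the lower confidence limit exceeds the performance goal of 62" per cent, "using a one-sided exact lower 97.4% confidence bound at one of three testing points". The sample-size paragraph of 11.1 also uses 97.4%. The Primary Endpoint Analysis then repeats the criterion "using a one-sided lower 94.5% exact confidence bound at one of the three testing points".
- **Counts.** "The method for testing the conversion success will follow these steps": 12/12 at the first look, 16 or 17 of 18 at the second, and at the third "21 of the 24 are successful (87.5% conversion rate), the trial will be deemed a success".
- **Failure cap.** "If at any point during the course of this study there are more than three (3) failures to convert a shockable rhythm" and, after a parenthesis, "due to the Jewel, the study will be stopped and deemed unsuccessful".

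The graph that summarises the design in 11.1 is not shown in the text available.

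**The concern.** The three descriptions should give one verdict for each result, and the stated operating characteristics should be those of that rule. Neither holds fully.

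The power figure matters most, because it does not depend on which description governs. If 87.5% is the true rate, readers are told the chance of missing the endpoint is 10%; under the written counts it is about 30%.

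The confidence level is printed with two values for one criterion, and the lower value would pass results that Steps 1 and 2 do not pass.

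At 24 subjects, the bound accepts a result that Step 3 does not name. The cap covers most of that conflict, but it counts only failures attributed to the device. That attribution is not defined in the visible text and appears in neither the endpoint nor the steps. In a non-blinded, single-arm study, it is better fixed before the result is known.

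**Working it through.** **Inputs.** Goal p0 = 0.62, anticipated rate p1 = 0.875, looks at 12/18/24, levels 97.4% and 94.5%, the counts and the cap (all 11.1; goal and 97.4% also 6.1). Assumed: independent subjects, one shock each, constant success rate p (q = 1 − p), and 24 treated subjects available.

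**1. Lower bounds.** The one-sided Clopper-Pearson bound for x of n at level c is the (1 − c) quantile of Beta(x, n − x + 1). For 12/12 at 97.4% it is 0.026^(1/12) = 0.738.

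| Result | 97.4% | Plan states | 94.5% |
|---|---|---|---|
| 12/12 | 73.8% | 73.7% | |
| 11/12 | 61.8% | | 66.8% |
| 17/18 | 72.9% | 72.8% | |
| 16/18 | 65.5% | 65.4% | |
| 15/18 | 58.8% | | 62.9% |
| 21/24 | 67.8% | 67.8% | |
| 20/24 | 62.8% | | 66.3% |
| 19/24 | 58.0% | | 61.6% |

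The plan's own bounds reproduce to within 0.1 point at 97.4%. The Pocock nominal one-sided level for these looks is 0.0258, which also fits 97.4%. At 97.4% the bound and the counts differ only at 20/24. At 94.5% they also differ at 11/12 and 15/18.

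**2. Written rule (counts).** Success probabilities by look, counting the sequences that reach it:

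- 12/12: p^12.
- 17 or 16 of 18, with at least one failure in the first 12: 12 p^17 q + (153 − 15) p^16 q².
- 15 of 18 with at least one failure in the first 12, then six successes: (816 − 20) p^21 q³. Since 15 + 6 = 21, no higher final count can be reached.

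At 0.875: 0.20142 + 0.40955 + 0.09415 = 0.70512, so power is 70.5%.
At 0.62: 0.003226 + 0.010848 + 0.001908 = 0.015982, so Type I error is 1.6%.

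The cap changes neither figure, because four failures already rule out 21/24. Solving for power 0.90 gives p = 0.919.

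**3. 97.4% bound as the rule, cap removed.** This adds 20/24 reached after continuing past both looks. Of C(24,4) = 10,626 sequences, 2,670 have at most two failures in the first 18, and a further 135 have none in the first 12. That leaves 7,821, so the addition is 7,821 p^20 q^4.

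At 0.875: 0.70512 + 0.13215 = 0.83727 (83.7%).
At 0.62: 0.015982 + 0.011488 = 0.02747 (2.7%).

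Power 0.90 would need p = 0.893. With the cap and its verdict applied, this rule returns to 70.5% and 1.6%.

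**4. Literal 94.5% bound (11/12, 15/18, 20/24).**

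- Type I error without the cap: 0.0270 + 0.0305 + 0.0041 = 0.0616 (6.2%). With the cap: 0.02696 + 0.03053 = 0.05749 (5.7%).
- Power without the cap: 0.5467 + 0.2841 + 0.0474 = 0.8782 (87.8%). With the cap: 0.5467 + 0.2841 = 0.8308 (83.1%).

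**5. How often 20/24 is in dispute at 97.4%.** If every failure counts toward the cap, the fourth failure must fall on subject 24: 796 p^20 q^4 = 1.3% at 0.875 and 0.1% at 0.62. If the cap never triggers, it is the 7,821-sequence term: 13.2% and 1.1%. These are the minimum and maximum; the plan gives nothing to place the true figure between them.

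**The case against.** A reader might infer that nothing in the plan ranks the bound against the counts, so that 20/24 could be called either way. The documents do not support that. The cap expressly gives a study verdict of unsuccessful after a fourth failure attributed to the device. Section 11.1 introduces the counts as the method of testing, and Step 3, the cap and the worked example with three failures in 24 all agree. What survives is narrower: the endpoint wording would still be met in a study deemed unsuccessful, and the case of a failure attributed elsewhere is left open. The missing graph might also settle the ranking.

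A reader might also infer that the Type I error is out of control. It is not under the written rule (1.6%), nor under the 97.4% bound without the cap (2.7%). Only the literal 94.5% exceeds 5%. That level appears once, while the printed bounds and Steps 1 and 2 fit 97.4%, so it looks like a slip.

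On power, the discussion that states 90% names no alternative, so the link to 87.5% is an inference from the sample-size paragraph. The 90% may also come from the normal approximation that 11.1 describes. Yet three-look Pocock approximations give 77.8%, 84.2% or 97.4%, depending on the variance used. Only a single-look approximation at one-sided 5% comes near (91.4%), and that is not the planned design. The simulations reported in 11.1 are said to confirm the Type I error; nothing is said of power after the move to exact methods.

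Finally, 24 treated subjects is an assumption. Section 7.1 limits enrolment to 24 and 8.2 expects about 30% of cases to need no shock, although section 6 can be read as enrolling until the treatment sample is met.

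**Conclusion.** The concern holds in three parts, in order of weight.

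1. **Power.** No reading of the success rule reaches 90% at 87.5%. The written rule gives 70.5%, and the most favourable variant (literal 94.5%, no cap) gives 87.8%. This rests on 87.5% being the intended alternative and on 24 treated subjects.
2. **Confidence level.** The single 94.5% contradicts 6.1, the sample-size paragraph and the worked bounds in 11.1. Its effect is real only if it is applied literally.
3. **20/24.** The endpoint wording and the counts conflict. With every failure counted toward the cap, the conflict has probability 1.3% at 87.5%. The 13.2% is a ceiling, not an estimate.

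The arithmetic is exact. The claim about ranking is limited to the visible text.

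**What to change.** - **Overall Type I Error Discussion (11.1).** Restate power as 70.5% at 87.5% and Type I error as 1.6% at 62% for the written rule, and state that 24 treated subjects are assumed.
- **Primary Endpoint Analysis (11.1).** Change 94.5% to 97.4%.
- **Sections 6.1 and 11.1.** Say that success is decided by the counts in Steps 1 to 3, and that the 97.4% bounds justify those counts and are not a separate criterion.
- **Failures.** State that every non-conversion after a Jewel shock in the treatment analysis counts as a failure for the efficacy verdict. Reconcile the attribution wording of the cap with that statement. Whether and when to stop remains the sponsor's decision, and a change to that wording may change when the study stops.

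If the sponsor prefers the 97.4% bound to govern, with 20/24 a success, the failure rule must be changed to match. That is a design change, not a clarification, and the figures to state would be 83.7% and 2.7%.

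The cost is a few sentences and no added subjects. The drawback is a less favourable stated power.
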